Patients will be recruited through BIDMC and BILH clinics and if necessary, through affiliated MAPNET clinics. Patients will be recruited via flyers/advertisements placed in clinic waiting rooms, public information sessions at the clinic about the project, and asking clinicians to hand out study flyers to subjects who they think may be interested. Patients will also be recruited by approaching the clinicians, and if they agree, then approaching the subject for consent into the study. Interested patients will be able to contact and call study staff for more information. ECS subjects will also be recruited from our IRB approved retinal imaging study where patients have provided consent to be recontacted about future studies via email (IRB 2019P000815). Subjects will be contacted by email only if they previously consented to this. If interested, they will then receive a phone screening questionnaire. Upon first contact, the study research assistant/coordinator will explain the study to patients. If they are interested in continuing, a brief initial telephone screen will be administered, assessing inclusion criteria. Those who agree to continue will be scheduled for an individual interview with the study research assistant at BIDMC or through Microsoft Teams to assure privacy.

In some cases, the consent procedure will occur remotely to allow only the screening and baseline portions of the study to occur via video conferencing. A written informed consent form that outlines what study procedures will occur remotely has been uploaded to RedCap. This consent form will be emailed to the participant ahead of a scheduled phone or Microsoft Teams video-conferencing call. During the phone/video call, a trained clinician or study research assistant will review the form with the participant (and, when applicable, with their legal guardian) in a private room in order to ensure HIPAA compliance. The research clinician or assistant will follow the same procedure as the in-person consent. All subjects must understand the requirements, risks, and benefits of the research protocol, which is approved by the Institutional Review Board BIDMC, before they are allowed to sign. Subjects must understand that they have the right to refuse participation at any time during the study. To more formally assess and document each subject's ability to give informed consent, the person obtaining consent will follow up the study description with an interactive questionnaire addressing the main points of the informed consent procedure via RedCap. Then, the participant may e-sign and date the RedCap consent form, after which the research clinician or assistant will do the same. A copy of the signed consent form will be emailed to the participant. When the participant is able to come into the laboratory for their first in-person visit, the PI, coinvestigator, or their representative will review the full (non-verbal) consent form with the participant and obtain a physical signature on the consent form.

All subjects must understand the requirements, risks, and benefits of our research protocol before they are allowed to sign. Subjects must understand what to do should they experience any discomfort during the course of the study. Subjects must understand that they have the right to refuse participation at any time during the study. To more formally assess and document each subject's ability to give informed consent, the person obtaining consent will follow up the description of the study with an interactive PowerPoint presentation addressing the main points of the informed consent procedure. The study investigator will ask the subject each question and document their response. Subjects who are unable to answer the questions, even after additional information is provided, will be excluded from the study. This process is designed to enroll only subjects who have the capacity to make the decision to participate and to prevent undue influence on the subject to enroll in the study by their physician. The PI, co-investigators, or their representative will obtain written consent after explaining the procedures. These individuals are certified by the PI that they have in depth understanding of the study and procedures. Only when the subject declares that they are comfortable with all aspects will the subject be allowed to offer consent. The informed consent form will be signed by the subject and a member of the study staff. All key personnel will have passed the web-based training course on the responsible conduct of research.

Because people who are recruited for this investigation display symptoms of psychosis, we will use the attached Assessment of Capacity form to assess ability to consent to participation. This form has been used in previous studies with schizophrenia at our center. The form prompts the investigator to assure that the subject is voluntarily choosing to participate in the study, has a factual understanding of the study, has an appreciation of the significance of the facts about research participation and is able to reason about his or her participation.

Subject Protection

Patients with schizophrenia, schizoaffective disorder may be considered a vulnerable population. The multi-step consent process involving both a phone screening and in-person visit, or secure remote process provide safeguards and opportunities for subjects to understand the study and choose whether or not to partake. Subjects will be questioned to confirm their understanding of the protocol and possible risks or adverse side effects of Sodium Nitroprusside, thus helping ensure that subjects with incomplete understanding do not unwittingly consent to the study. Finally, we will also complete a one-page Assessment of Capacity form to provide informed consent. We will assure subjects both on the informed consent form and in person that refusal to partake in the study or drop-out from the study at any point has no impact on continued services from their current clinic or at BIDMC. Clinical interviews will be performed by a trained clinical staff who will be able to reassure subjects or if necessary, provide counseling if they are distressed. Subjects will be forewarned throughout the pre-screening and screening process that the protocol involves sitting in a chair for up to 5 hours, and that they may take breaks at any time. Breaks will be offered to subjects regularly, though they may decline to take them.

Again, if during the consent process or any study visit, study staff notice the subject expressing suicidality, homicidality appearing agitated or distressed, or if they score 4 or higher on the PANSS question G6 "Depression", they will be instructed to pause the protocol and immediately contact the investigator (Drs. [name] or [name], all trained psychiatrists), who will perform a safety assessment, contacting outpatient providers or emergency services as deemed necessary.

B7. STUDY LOCATION

Privacy

Screening will be performed by phone or via Microsoft Teams and we will assure that the participant is located in a place where they can securely answer any sensitive questions. Initial screening for the study will take place over the phone/Microsoft Teams via a screening questionnaire. At the start

of the phone call, the potential subject will be forewarned of the possibility of sensitive questions in the screening questionnaire. They will be offered the choice to defer the phone screening questionnaire to a different time if they are uncomfortable answering questions over the phone at that time. Assessments and procedures for the study will take place in private suites and rooms at BIDMC, and OCTA assessments will take place at Massachusetts Eye and Ear's, which will afford protection against a participant's violation of privacy. Some of these assessments can be performed virtually. We will also limit the information that is being collected to only the minimum amount of data necessary to accomplish the research purposes.

Physical Setting

Urine toxicology screen, urine pregnancy test, consenting, screening and baseline assessments will take place in [name] lab space at BIDMC. Subsequent medical screening (blood tests, vital signs, EKG) and SNP infusion visits will occur in the BIDMC Clinical Research Center. The visits will be completed with a single subject at a time, ensuring privacy. Data will also be stored at BIDMC.

B8. DATA SECURITY

To ensure confidentiality, the entry of self-reported data into electronic format will be identified only by subject number, visit number and date of visit. By recording the study data in this manner, the information can be considered de-identified and therefore compliant with the Standards for Privacy of Individually Identifiable Health Information ("Privacy Rule") of the Health Insurance Portability Act of 1996 (HIPAA). Any data that is transmitted electronically will be fully encrypted and password protected. Subjects' names will never be entered into a database; each will uniquely be identified by an ID number. Consent forms and any study measures that are completed on paper will be kept and filed in separate locked office cabinets accessible only to lab personnel ([name]). Computer data files are labeled using arbitrary identification codes to preserve confidentiality as well.

A master data file containing the associations between each participant's demographic information (e.g., age and gender) and their unique identification code will be kept on a password protected computer. This information is used to report the gender and age of the subject sample in publications, required by many journals. Only lab research will have access to this computer and this file.

Data collected by a computer will be stored on computers within the laboratory and also stored in a backup format on the lab's RAID array and/or on external media such as recordable DVDs or encrypted external hard drive. No identifying information will be kept in relation to these data. Data collected by questionnaire or written record by the experimenter will be kept in a locked office in the laboratory along with the Informed Consent Forms. Only lab research personnel will have access to informed consent forms or other such personal information about the subject.

The data collected from these studies will be conducted in private locations where subjects can be assured their information is collected privately and in a strictly confidential manner. All consent forms, questionnaires and related hard copy forms with personal identifiers will be securely stored in a file in a locked office. The files in this office are accessible only to lab research personnel. Each participant's computerized data will be labeled with a unique identification code that bears no resemblance to the participant's name. All behavioral, SS-OCTA and routine laboratory test data will be stored on computer hard drives in the laboratory. Back-ups of all data files will be stored on encrypted external storage devices within the laboratory (e.g., external hard drives, CD-R). Individually identifiable data will not be released to anyone outside of the lab unless required by law and/or necessary for oversight purposes.

E	B9 Multi-Site Studies	
	Is the BIDMC the coordinating site?	
	Is the BIDMC PI the lead investigator of the multi-site study?	☐ Yes ☐ No

B10 Dissemination of Research Results

We appreciate the time and effort that our research subjects provide for the advancement of medicine. We will acknowledge our subjects in manuscripts that arise from this work. We will provide our participants with our contact information if they are requesting study progress. At the completion of the study, we will send each participant a letter thanking them and giving them an update regarding our findings.

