SS-OCTA: Images will be obtained using the Zeiss PLEX Elite 9000, which is a quick, inexpensive, and non-invasive method for acquiring retinal images with an axial resolution of ~5µm and a scan depth of 3.0mm. Automated layer segmentation provides four horizontal depth-resolved retinal slabs: superficial (SRL), deep (DRL), outer retinal layer (ORL) and the choriocapillaris. Participant images will be excluded for low signal strength (≤6), blink artifacts, doubling artifacts, media opacity obscuring visualization of the vasculature, and/or segmentation errors. Manual segmentation editing will be conducted to ensure proper layer assessment. Microvessels for the SRL, DRL, and choriocapillaris slab will be processed using a custom semiautomated algorithm we developed to rapidly quantify several vessel parameters including vessel density, length, diameter, and capillary network. All images will be independently analyzed and compared among study subjects by two graders blinded to the group assignment.

Outcome: Primary outcomes include the change in PANSS positive and negative scores (2hrs, 5hrs, 1wk, 2wk, and 4wks) in the SNP group compared to placebo. The secondary outcomes include the change in overall cognition (0hr, 1wk, 2wk, and 4wks) and retinal microvascular measures (0hr, 5hrs), as well as examining the relationship between baseline or change in retinal vessel measures or CRP and the change in psychosis symptoms and cognition after SNP treatment compared to placebo.

SNP Treatment Protocol

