Baseline demographic details will be compared between the SNP and placebo groups using independent-samples t tests or Mann-Whitney U tests where appropriate using R software. Categorical data will be compared using chi-square tests. Effect sizes will be provided using Cohen's d. The primary outcome (PANSS) will be analyzed using a 2 (treatment group) × 5 (time point) mixed analysis of variance (ANOVA). Analyses of secondary outcome measures will be compared using a 2-group x 4 time point mixed ANOVA for cognition and a 2 x 2 for retinal measures. The relationship between baseline or change in retinal vessel measures or CRP and change in PANSS scores or cognition will be performed using Pearson's (parametric) or Spearman's (non-parametric) correlation.

C. Subject Selection

Population: Men and women, 18-60 years of age, from diverse background, symptomatic, with early course schizophrenia, and meet all study inclusion and exclusion criteria.

Inclusion criteria for ECS patients are: a DSM-V diagnosis of SZ or schizoaffective disorder with ≤5 years from the onset of psychosis and up to 2 years of lifetime exposure to antipsychotics, total score of ≥55 on the PANSS with a score of ≥3 on 1 or more PANSS Positive Scale items (delusions, conceptual disorganization, hallucinatory behavior, suspiciousness, or unusual thought content) and/or score of ≥3 on the CGI-S scale, taking antipsychotic for 8 weeks with a stable dose of 4 weeks (no medication change will be allowed during the trial), English proficiency, understands and is able, competent and willing to give informed consent in accordance with the International Conference on Harmonization Good Clinical Practice Guidelines.

Exclusion criteria are:

- Presence of renal, hepatic, cardiac, hematologic, neurologic impairments or abnormal physical exam.
- Presence of retinal disease (myopia >4.0 diopters)

- Baseline systolic BP <100mmHg or symptomatic orthostatic hypotension (systolic BP <90 mmHg or diastolic BP <60 mmHg) with any of the following: lightheaded or dizzy, blurry vision, weakness, syncope, confusion, nausea.
- Pregnant or breastfeeding (pregnancy test at screening visit and prior to randomization).
- Abnormal laboratory testing (see appendix)
- Treatment with medications that may interfere with the metabolism or excretion of SNP or are associated with drug-drug interactions (see list of medications below).
- Prior history of intolerance to SNP
- Currently taking clozapine or chlorpromazine

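### The reference rating for the primary PANSS change is not fixed, so as written the 2 h and 5 h change may be measured from an earlier and, for some participants, remote rating

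*Combined protocol and SAP*

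**What the plan says.** Four places bear on the reference rating.

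- **B3.A, Outcome.** The primary outcome is "the change in PANSS positive and negative scores (2hrs, 5hrs, 1wk, 2wk, and 4wks"), compared with placebo. The next sentence gives the secondary outcomes as "the change in overall cognition (0hr, 1wk, 2wk, and 4wks) and retinal microvascular measures (0hr, 5hrs"). Only PANSS lacks a 0hr point.
- **B3.B, Statistical Considerations.** PANSS "will be analyzed using a 2 (treatment group) × 5 (time point) mixed analysis of variance (ANOVA"). The secondary outcomes get a "2-group x 4 time point mixed ANOVA for cognition and a 2 x 2 for retinal measures". No baseline covariate is named.
- **B7, Physical Setting.** Baseline assessments are placed in the investigator's lab space. Then: "Subsequent medical screening (blood tests, vital signs, EKG) and SNP infusion visits will occur in the BIDMC Clinical Research Center".
- **B6, Recruitment and Consent.** Remote consent is permitted in some cases "to allow only the screening and baseline portions of the study to occur via video conferencing". For those participants a first in-person visit comes later.

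The only PANSS rating before dosing that the text names is the eligibility score in B3.C (total of at least 55). The pre-infusion items in the infusion protocol cover positioning, the IV line, nicotine replacement, ECG and vital signs, but no symptom rating.

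**The concern.** The trial looks for a symptom effect within hours of a single infusion. A change on that scale is best measured from a rating taken just before dosing, in the same setting as the ratings that follow. If the reference is an earlier visit, the change at 2 h also contains whatever happened between that visit and the infusion. If it was rated by video, it also contains any difference between rating modes, for those participants only. If it is the eligibility score, patients were selected on it, and regression to the mean enters the change.

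Two things are at stake. Group comparisons of change scores would carry avoidable noise in a trial of 32. The planned correlations of PANSS change with retinal measures or CRP could include change from before any drug was given; B3.B does not say they are compared between arms, so randomisation need not protect them.

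**Working it through.** **1. Do the time points and the models agree?**

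| Outcome | Times listed in B3.A | Count | Time levels in B3.B |
|---|---|---|---|
| PANSS | 2 h, 5 h, 1, 2, 4 wk | 5 | 5 |
| Cognition | 0 h, 1, 2, 4 wk | 4 | 4 |
| Retinal | 0 h, 5 h | 2 | 2 |

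The secondary models match only if 0 h is counted. The primary model matches only if it is not. As written, no PANSS rating from before dosing enters the primary model, either as a level or as a covariate.

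**2. The plan's own power figure.** Inputs from B3.B: 16 per arm, difference 10, SD 6, two-sided 0.05, two-sample t-test. Noncentrality = 10 / (6 × √(2/16)) = 4.71 on 30 df. Power is 99.5% (99.7% by normal approximation), so the stated figure of more than 80% holds as a lower bound. With SD 6 the difference detectable at 80% power is 6.15 points. Power for 10 points falls below 80% only when the SD reaches about 9.8. The plan does not say whether SD 6 is that of a single rating or of change, so both readings follow.

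**3. Reading A: SD 6 is the SD of one rating.** The correlation r between reference and follow-up is assumed; the documents give none. SD of change = 6 × √(2(1 − r)).

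| r | SD of change | Detectable difference, 80% power | Change variance, 72(1 − r) | Covariate-adjusted variance, 36(1 − r²) |
|---|---|---|---|---|
| 0.9 | 2.68 | 2.75 | 7.2 | 6.84 |
| 0.8 | 3.79 | 3.88 | 14.4 | 12.96 |
| 0.7 | 4.65 | 4.76 | 21.6 | 18.36 |
| 0.6 | 5.37 | 5.49 | 28.8 | 23.04 |

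If a same-day, same-mode reference gave r = 0.9 and an earlier one r = 0.7, the variance of change would be 21.6 / 7.2 = 3 times as large. Adjusting for the reference as a covariate gives a smaller variance than subtracting it at every r shown.

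**4. Reading B: SD 6 is the SD of same-day change.** Add an assumed drift SD between reference and infusion: SD = √(36 + drift²).

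| Assumed drift SD | SD of change | Power, 10 points | Power, assumed 6 points |
|---|---|---|---|
| 0 | 6.00 | 99.5% | 78.1% |
| 4 | 7.21 | 96.7% | 62.5% |
| 6 | 8.49 | 89.7% | 49.0% |
| 8 | 10.00 | 78.1% | 37.6% |

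An assumed 5-point mode shift in half the patients adds 0.5 × 0.5 × 25 = 6.25 to the variance. With drift SD 6 the SD is then √78.25 = 8.85, and power for 10 points is 87.2%.

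**5. Correlations.** Under Reading B, drift unrelated to the biomarker shrinks a correlation by 6 / √(36 + drift²): 6 / 7.21 = 0.83 at drift SD 4, and 6 / 8.49 = 0.71 at drift SD 6. Drift that is related to the biomarker would instead add association that has nothing to do with treatment.

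**6. Which tests are exposed?** Change at time t is the score at t minus one reference value per patient. That value is constant over the five times, so it cancels from the group × time interaction. It remains in the group main effect on change scores and in any comparison of change at a single time. B3.B does not say which effect is primary, or whether raw scores or changes are analysed.

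**The case against.** The strongest reply is that a list of times at which change is measured need not repeat the reference point. The study design figure is not shown, and the Schedule of Events and flow chart that B3.A mentions are not in the readable text; any of them may list a pre-infusion PANSS. The text also points to assessment before dosing on the infusion day: 0hr cognition and retinal measures, safety scales before the infusion (B5), vital signs labelled as pre-infusion baseline, and research staff giving rating scales at the infusion visit. Drift is limited by the required stable antipsychotic dose. All of this stands, and it is why the point concerns an undefined reference rather than a demonstrated error.

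A reader might go further and infer that the 2 h change does mix in days of fluctuation and a switch from video to in-person rating. The documents do not support that. No interval is given, no section says a PANSS is rated by video, and the B6 sentence concerns remote consent in some cases and names no scale. Nor do they support barring remote cognitive baselines, since 0hr cognition is already listed.

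The magnitudes also rest on assumptions. Every SD in Reading A is below the plan's own 6, and the threefold variance ratio is simply the choice of 0.9 against 0.7.

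What the reply does not remove is that the readable text leaves the reference for the primary outcome open, and that the 2 × 5 model has no place for it.

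**Conclusion.** The point holds as a gap in definition with a cheap remedy. Followed as written, the reference for the 2 h and 5 h PANSS change may be an earlier and, for some participants, remote rating.

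The consequence is limited. Drift and mode differences fall on both arms alike in expectation, so the comparison with placebo is not biased on average. Power for 10 points stays above 80% unless the SD of change reaches about 9.8, which under Reading B needs a drift SD of about √(9.77² − 36) = 7.7. The possible loss lies in group comparisons of change scores, mainly for effects well below 10 points, and in the biomarker correlations. Its size cannot be set from the documents, because the correlations, drift and mode shift used above are all assumed. A reader might infer that the primary comparison is biased or underpowered for its stated target; neither follows.

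**What to change.** - **B3.A, Outcome:** specify a 0hr PANSS, rated in person at the Clinical Research Center on the infusion day before the infusion starts, and define it as the baseline for all PANSS change scores.
- **B3.B:** include that rating in the primary model, as a covariate or as a sixth time level.
- **B6:** exclude this outcome-baseline PANSS from the video option, and keep the earlier PANSS for eligibility only.
- If the design figure or schedule already shows a pre-infusion PANSS, align these three places with it.

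The cost is protocol wording and at most one more PANSS interview, with a longer infusion visit, on a day when the scale is already given twice.
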